## **1.4 Risk/Benefit assessment**

### **1.4.1 Known potential risks**

Levosimendan is a marketed drug, which has been widely used in clinical treatment of acute and chronic heart failure, as well as some types of acute right heart failure in severe patients [10]. The purpose of this study was to observe the effects of levosimendan on right heart function in patients with ARDS on mechanical ventilation, except for possible adverse reactions in the drug instructions, and the drug itself does not pose risks to patients. The contents of the study were all within the scope of routine diagnosis and treatment for patients with mechanical ventilation, and blood drawing examination was also a routine examination item for patients with severe illness, so the frequency of examination would not be increased. In this study, sampling and transesophageal ultrasound were conducted to monitor right heart function, which was completed during the sedation and analgesia of patients with mechanical ventilation, without causing additional psychological or physical pain to patients. Transesophageal ultrasound was performed by clinicians participating in the study, so there was no additional cost.

### **1.4.2 Probability of injury**

the possibility of subject harm may involve adverse effects associated with levosimendan. Clinically possible adverse effects are increased heart rate or temporary and slight decrease in blood pressure, which can be treated with dose reduction or withdrawal and symptomatic management.

### **1.4.3 Degree of injury**

An increase in heart rate or a temporary slight drop in blood pressure is considered mild injury and can be treated appropriately.

### **1.4.4 Known potential benefits**

The occurrence of ARDS related right heart failure is not uncommon, and the

combination of acute right heart failure will lead to hemodynamic failure and significantly increase mortality in mechanical ventilation ARDS patients. At present, there is no clear and effective drug for ARDS right heart failure in clinical practice, and there is also a lack of relevant clinical evidence. The results of this study will provide certain clinical evidence for drug treatment of right heart failure in patients with mechanical ventilation ARDS, and may even help to reduce the mortality of ARDS patients and improve the prognosis.

Of course, the study design for this subject will minimize the need for subjects to be exposed to risk. First, avoid all contraindications of levosimondan use in the drug label and exclude patients who already have rapid arrhythmia or hypotension. The management of possible risks has been elaborated in the medication procedure. Vital signs of patients will be monitored in real time throughout the experiment, and adverse reactions will be handled according to the experimental procedure to minimize risks.

#### **1.4.6 Discussion**

ARDS is often complicated by right ventricular dysfunction (RVD), the incidence of which can be as high as 64%. The pathogenesis includes elevated pulmonary vascular resistance and right ventricular systolic dysfunction [1-3]. The fatality rate of ARDS patients with RVD increased significantly from 30.6% to 56.3%[4,5]. For ARDS patients with right heart failure, currently available drugs include dobutamine and Milrinone, but dobutamine has a high risk of rapid malignant arrhythmia, increases myocardial oxygen consumption, and large doses will increase the proportion of body and lung circulation, leading to systemic hypotension, which is not conducive to the treatment of ARDS patients with right heart failure [14]. Milrinone also has the effect of increasing myocardial contractility, but its application is limited due to systemic hypotension [14]. While levosimendan increases myocardial contractility, it does not increase myocardial oxygen consumption and does not lead to malignant arrhythmias. Many animal experiments have shown that levosimendan can reduce pulmonary circulation resistance, protect myocardium

during myocardial ischemia, improve right ventricular/pulmonary artery coupling, and improve myocardial energy metabolism. Compared with dobutamine and Milrinone commonly used in clinical practice, levosimendan has more advantages and has fewer side effects on patients [14]. Therefore, the purpose of this study is to provide a more powerful research basis for the use of levosimendan in ARDS patients with right heart failure. Because the drug itself has few side effects of arrhythmia and hypotension, and the protocol has fully considered the management of adverse reactions, the risk to subjects will be minimized even if there is no clinical benefit.

## **2. Study objective/end point**

The main objective is to (confirm) about whether or not the leosimendan improve mechanical ventilation in patients with ARDS right heart function.

secondary objective is to exploratory whether or not levosimendan reduces mechanical ventilation in patients with ARDS mortality

Primary endpoint: the incidence of RVD after 48h ending of randomization

Secondary endpoint: (1): TAPSE, S ', FAC, RVEDA/LVEDA PVR, RV-PA coupled CI, SVI, SVR, ScvO2 SOFA score after 48h ending of randomization. (2) 28-day mortality rate, in-hospital mortality rate.

## **3. Research design**

### **3.1 Overall Design**

Prospective, multicenter, randomized controlled study. According to the random allocation method, the subjects were divided into experimental group and control group; The control group was injected with 50ml 5% glucose for 24h, and the experimental group was injected with 12.5mg levosimendan for 24h according to the experimental protocol. Right ventricular function was compared between the two groups before and 48h after medication: Right ventricular area change fraction (RV FAC), tricuspid annulus systolic displacement (TAPSE), tricuspid annulus systolic S 'velocity (S'), right ventricular end-diastolic area/left ventricular end-diastolic area (RVEDA/LVEDA), pulmonary circulation resistance (PVR), right ventricular - pulmonary artery coupling (RV-PA), heart index (CI), Per Bo index (SVI), systemic

resistance (SVR), central venous oxygen saturation (ScvO2). SOFA score of patients with mechanical ventilation ARDS treated with levosimendan 48h after medication was evaluated, mortality rate at random 28 days, and all-cause in-hospital mortality.

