Exclusion criteria	
1) Pregnant or lactating women;
 
(2) Chronic cardiac dysfunction, pulmonary hypertension and/or right ventricular enlargement caused by chronic cardiopulmonary disease, cardiogenic shock or after major cardiac surgery before ARDS;
 
3) right ventricular myocardial infarction;
 
4) Uncorrected hypotension, hypoxemia and hypercapnia, or acid-base balance disturbance
 
5) Mechanical ventilation driving pressure <math>\geq 18\text{cmH}_2\text{O}</math> before randomization
 
6) Rapid arrhythmia;
 
7) pericardial tamponade;
 
8) Pulmonary embolism;
 
9) severe renal insufficiency;
 
10) severe liver insufficiency;
 
11) Failure to sign informed consent;
 
12) known allergy to the test drug;
 
13) Patients who have participated in other clinical trials within 30 days

Intervention	Patients will be randomized to treatment group A: intravenously injected levosimendan 12.5mg with 5% glucose injection 50ml configuration at 2ml/h for 24h, or treatment group B: control group with 5% glucose injection 2ml/h for 24h.

Evaluation criteria: Primary endpoint: Secondary end point: Safety evaluation	Primary endpoint: The rate of RVD occurrence within 48 hours after randomization. secondary end points: 1) Changes in the following indexes were assessed 48h after random administration including : TAPSE, S ', RV FAC, RVEDA/LVEDA PVR, RV-PA coupling, CI, SVI, SVR, ScvO2 SOFA scoring 2) Mortality at 28 days after randomization and in hospital
Statistical Methods:	Sample size: 23 cases in the experimental group and 23 cases in the control group. Considering the 20% shedding rate, the statistical sample size was 29 cases in the experimental group and 29 cases in the control group, and a total of 58 subjects were enrolled.  Primary endpoints: incidence of RVD 48h after randomization  Safety endpoints:  Safety endpoints are those where subjects have severe adverse reactions related to the drug that are persistent and cannot be corrected according to the protocol
Study duration	2023.02-2025.12
Subject attendance time	From the time subjects were recruited to the time each subject completed all follow-up visits
Research unit/location	Wuhan Union Medical College Hospital, the First Affiliated Hospital of Zhengzhou University, Henan Provincial People's Hospital
Name, qualifications and contact information of the principal investigator	
	[name], [contact], has obtained the GCP Certificate

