## 6. Research steps

- (1) Patients eligible for inclusion in the study were screened and informed consent was signed.
- (2) Patients were randomly assigned to the experimental group or the control group. Vital signs and hemodynamic parameters were recorded 1 hour before administration, and related indexes such as cardiac function and pulmonary circulation were detected by transesophageal ultrasound, as well as arterial blood gas, central vein blood gas, blood routine, liver and kidney function, electrolyte, myocardial enzyme profile and BNP were detected by blood sampling.
- (3) According to the study protocol, all subjects in the two groups began administration at 8am, and 8am vital signs, arterial blood gas, central vein blood gas,

blood routine, liver and kidney function, electrolytes, myocardial enzyme profile and BNP during medication period and the first 24 hours after medication completion were recorded. The related indexes of cardiac function, pulmonary circulation and hemodynamics were monitored by transesophageal ultrasound. Study withdrawal/early termination: Family members refuse to continue treatment if: Family members withdraw from the study; In the presence of experimental-related serious adverse reactions.

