## **7 Evaluation**

### **7.1 Primary and Secondary Endpoints/Outcome Evaluation Primary outcome:**

Rate of RVD at 48h randomized administration. Secondary outcome: 48h after random administration, the following indicators were assessed. Other indicators of right cardiac function were: TAPSE, S', FAC, RVEDA/LVEDA PVR RV-PA coupling CI, SVI, SVR, ScvO2 SOFA score after random 28-day mortality, in-hospital mortality

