## **9. Statistical analysis and statistical methods**

- (1) Case enrollment analysis: The total number of enrolled and completed cases in each center was listed, and three analytical data sets (FAS, PPS, SS) were determined. List the cases of shedding and elimination and their causes.
- (2) Demographic data and baseline analysis: descriptive demographic data and other baseline characteristic values; The number of cases, mean value, standard deviation, median, minimum value and maximum value of measurement data were calculated. Count and grade data calculation frequency and component ratio.
- (3) Effect analysis: CMH- $\chi^2$  test considering central effect was used for comparison between groups. t test or Wilcoxon rank sum test were used to compare the measures between groups.  $\chi^2$  test or Fisher's exact probability method were used to compare the classification indexes between groups. Rank data were obtained by Wilcoxon rank sum test or CMH- $\chi^2$  test. Survival data will be described using Kaplan-Meier curves and life tables. A nonparametric confidence interval for the median lifetime is calculated. Linear rank tests (logrank test and Wilcoxon test) were used to compare

survival between the treatment group and the control group. The Cox risk model was used to analyze the potential influence of covariates (predictors). Multivariate logistic regression was used to analyze dichotomous outcomes, such as recurrence rates, and this multivariate model would identify the most significant predictors. Logical or proportional advantage models will be used to adjust for prognostic factors. Precise confidence intervals will be calculated for the binary event incidence.

(4) Safety analysis: the incidence of adverse reactions was calculated; The sub-system lists the frequency and frequency of adverse reactions and calculates the percentage; A detailed list of adverse event cases; A detailed list of adverse event cases; The number and rate of "abnormal normal conversion" or "abnormal intensification" of laboratory indicators, electrocardiogram and physical examination after the test; List laboratory indicators, electrocardiograms, abnormal cases of physical examination and clinical explanations.

(5) Statistical software and general requirements use SAS software for analysis. All statistical tests were two-sided, and  $P \leq 0.05$  would be considered statistically significant.

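### Section 3.1 words the 48 h SOFA score as a levosimendan-arm, post-dose measure, while the abstract and sections 2, 7.1 and 9(3) imply a two-arm endpoint: a minor inconsistency in one secondary endpoint

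*Protocol*

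**What the plan says.** Section 3.1 (Overall Design) has two consecutive statements. The first covers the echocardiographic and haemodynamic indices: "Right ventricular function was compared between the two groups before and 48h after medication". Its list runs from RV FAC to ScvO2 and does not include SOFA. The second gives SOFA its own wording: "SOFA score of patients with mechanical ventilation ARDS treated with levosimendan 48h after medication was evaluated". The same sentence goes on to 28-day mortality and in-hospital mortality.

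Elsewhere in the protocol:

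- The abstract, under the evaluation criteria, introduces the secondary list with "Changes in the following indexes were assessed 48h after random administration including". SOFA closes that list.
- Section 2 has "SOFA score after 48h ending of randomization" as a secondary endpoint, with no arm named.
- Section 7.1 has "Secondary outcome: 48h after random administration, the following indicators were assessed". SOFA is among the indicators, again with no arm named.
- Section 9(3) states that "t test or Wilcoxon rank sum test were used to compare the measures between groups".
- Section 6 states that "Vital signs and hemodynamic parameters were recorded 1 hour before administration". It adds blood gases, blood routine, and liver and kidney function, and it repeats most of these in both groups during dosing and for the first 24 h afterwards. SOFA is not named there.

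**The concern.** The protocol gives one endpoint three descriptions: a change (abstract), a 48 h value in the trial population (sections 2 and 7.1), and a post-dose value in levosimendan patients (section 3.1). Only the first two allow a randomised comparison. A post-dose score in one arm can show neither a difference between arms nor a change within the arm.

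Who is scored, and when, is a matter of data collection. A statistical analysis plan can choose between value and change, but it cannot recover a score whose components were never recorded. A site working from sections 3.1 and 6 alone would find no instruction to score controls, or to score anyone before dosing.

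**Working it through.** No figure in the protocol depends on the SOFA wording, so the check is mainly a comparison of texts.

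**The protocol's own figure, to confirm that it is untouched.** Section 3.2 uses a difference of 20%, an SD of 20%, two-sided alpha 0.05 and power 0.9. By normal approximation, n = 2 × (1.960 + 1.282)² × (20/20)² ≈ 21.0, so 22 per arm. The t-based solution is 22.02, so 23 per arm. With 20% dropout, 23 / 0.8 = 28.75, so 29 per arm and 58 in total. The stated figures reproduce, and SOFA enters none of them.

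**The SOFA texts side by side.**

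| Place | Who | When | Value or change |
|---|---|---|---|
| Abstract | no arm limit | 48 h | change |
| Section 2 | no arm limit | 48 h | value |
| Section 3.1 | levosimendan patients | 48 h after medication | value |
| Section 7.1 | no arm limit | 48 h | value |
| Section 9(3) | between groups (measures in general) | not stated | not stated |
| Section 6 | SOFA not named | SOFA not named | not applicable |

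**Arm.** Section 3.1 stands alone. It does not say that controls are left out. That is inferred from the contrast with the preceding statement, which does name both groups.

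**Pre-dose score.** Only the abstract needs one to define the endpoint. Sections 2 and 7.1 ask for the 48 h score, and in a randomised trial two arms can be compared on that without a baseline.

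**What could be rebuilt from section 6.** The protocol does not spell out SOFA. I assume its usual six components: respiratory, coagulation, liver, cardiovascular, neurological and renal. Blood gases, blood routine, liver and kidney function and vital signs supply most of these, in both groups, before and after dosing. Two inputs are not listed: a neurological score, and the use of vasoactive drugs. Section 5.1 allows norepinephrine and dobutamine, but section 6 does not list their recording.

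**Time origin.** Section 2 counts from randomisation, section 7.1 from administration and section 3.1 from medication. Section 5.1 starts the infusion at 8 am after randomisation. If that is the next 8 am, the first two origins can differ by up to almost 24 h. If section 3.1 means the end of the 24 h infusion, its time point is 24 + 48 = 72 h after the start. Section 6 stops at 24 + 24 = 48 h after the start, which favours counting from the start.

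**Share of the endpoints affected.** The 48 h secondary list is TAPSE, S', FAC, RVEDA/LVEDA, PVR, RV-PA coupling, CI, SVI, SVR, ScvO2 and SOFA. SOFA is one of 11.

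**The case against.** The strongest reply is that this is rough English and not a design rule. Section 3.1 opens by calling the study randomised and controlled, and it describes two groups. The sentence in question also carries mortality. Taken literally, it would make mortality a single-arm endpoint too, against the secondary objective in section 2, which asks whether levosimendan reduces mortality. The abstract and sections 2, 7.1 and 9(3) are all compatible with scoring both arms. Section 6 does not list mortality either, so its silence on SOFA does not show that SOFA would go unrecorded. All of this stands, and it is why the point is minor.

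A reader might go further and infer that the trial will hold no control SOFA and no pre-dose SOFA, so that a comparison has no power. The documents do not support that. The inference takes one sentence as overriding every other section, and section 6 collects most of the components in both groups before and after dosing. Power figures for a two-arm SOFA comparison would not help, because the protocol gives no SOFA effect or SD and they would describe any t test of this size.

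The objection does not remove two things. Section 3.1 contradicts the endpoint sections as written, and nothing in section 6 ensures a complete score in either arm.

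**Conclusion.** The point holds as a minor internal inconsistency in one secondary endpoint. Section 3.1 names levosimendan patients after medication. The abstract asks for a change, sections 2 and 7.1 for a 48 h score without arm restriction, and section 9(3) for a comparison between groups. The missing pre-dose score conflicts with the abstract only. The primary endpoint, the sample size of 58 and the randomisation are unaffected, and no stated number changes.

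This rests on two judgements: that the sentence in 3.1 is probably loose wording, and that SOFA is scored from its usual components. If sites did follow 3.1 and 6 literally, the practical loss would be the components not listed, since the others could be taken from recorded data in both arms.

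**What to change.** 1. Reword the last sentence of section 3.1 so that SOFA, 28-day mortality and all-cause in-hospital mortality are evaluated in all randomised patients of both groups.
2. In section 6, add SOFA to the items recorded before dosing and at 48 h in both groups. Name the components not now listed: a neurological score and vasoactive drug use.
3. Use one definition in the abstract and in sections 2, 3.1 and 7.1: the 48 h SOFA score compared between groups with adjustment for the pre-dose score. This also settles value against change. If Y48 = a + bX + τT, where X is the pre-dose score and T the arm, then Y48 − X = a + (b − 1)X + τT, so the treatment effect τ is the same either way.
4. Count 48 h from the same origin in every section.

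The cost is a short bedside scoring at two time points, at most 58 × 2 = 116 scorings, plus recording of the few components not now listed. It needs no extra patients and changes no treatment rule.

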### **3.2 Sample size**

After discussion by clinical experts and combined with the literature results, it is expected that the mean difference and standard deviation between the experimental group and the control group in this study are 20% and 20% respectively.  $\alpha=0.05$  (bilateral), power=0.9, the proportion of experimental group and control group was 1:1, the number of cases meeting the statistical requirements of the experimental group and control group were 23 cases each. Considering the 20% shedding rate, the statistical sample size was 29 cases in the experimental group and 29 cases in the control group, and a total of 58 subjects were enrolled.

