dobutamine in acute right heart failure [8]. At present, relevant clinical studies have reported that levosimendan can be used in acute right heart failure caused by different causes, including a single-center randomized controlled study that reported that levosimendan can do work in the right ventricle of patients with septic ARDS, and has beneficial hemodynamic effects [9,10]. However, there is limited clinical experience in the treatment of right-heart dysfunction in patients with ARDS on mechanical ventilation and lack of high-quality clinical evidence. Therefore, multi-center randomized controlled studies are needed to obtain more and higher level of clinical evidence support, so it is necessary to carry out this clinical study.

In addition, the ratio of right ventricular end-diastolic area to left ventricular end-diastolic area (RVEDA/LVEDA) was used to evaluate ARDS RVD in the past, but this index cannot fully reflect right ventricular dysfunction. Right Ventricular Fractional Area Change (RV FAC) is significantly correlated with right ventricular end-diastolic area, and is more reflective of right ventricular systolic function [11]. In addition, lateral systolic displacement (TAPSE) of the tricuspid ring is also an important indicator of right ventricular systolic function. Therefore, in this study, RV expansion (RVEDA/LVEDA  $> 0.6$ ), TAPSE  $< 16\text{mm}$ , tricuspid ring systolic S 'velocity (TS  $< 10\text{cm/s}$ ) or RV FAC  $< 35\%$  represented RVD, and the incidence of RVD was used as the primary outcome indicator. Due to the poor right voice window in patients with mechanical ventilation, the evaluation of right heart function is limited. Therefore, from the perspective of practicality and operability in critical care medicine, this study uses transesophageal ultrasound to minimize the influence of lung gas on the right ventricular window, evaluates the right ventricular function in patients with mechanical ventilation ARDS, and discusses the influence of levosimendan on ARDS RVD and its relationship with prognosis, hoping to provide evidence support and useful reference for drug treatment of ARDS associated RVD.

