### **4.2 Inclusion Criteria**

Each subject must meet all inclusion criteria to be eligible to participate in the study.

- (1) Patients who have agreed to participate in the clinical trial and signed informed consent;
- (2) Age 18-80 years old, gender unlimited;
- (3) Patients with ARDS requiring mechanical ventilation;
- (4) Acute right ventricular dysfunction due to ARDS;

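### The stated power of 0.9 is for a difference in means of an unnamed variable; it does not apply to the yes/no primary endpoint, RVD at 48 h

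*Protocol*

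**What the plan says.** Section 3.2 states that "the mean difference and standard deviation between the experimental group and the control group in this study are 20% and 20% respectively". With two-sided alpha 0.05, power 0.9 and 1:1 allocation it arrives at 23 per arm, and a 20% dropout allowance takes this to 29 per arm, 58 in all. The variable with that mean difference and SD is not named.

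The primary endpoint is a proportion wherever it appears:

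- Abstract, evaluation criteria: "The rate of RVD occurrence within 48 hours after randomization".
- Section 1.1.1, after RVD is defined by echocardiographic cut-offs joined by "or": "the incidence of RVD was used as the primary outcome indicator".
- Section 2: "the incidence of RVD after 48h ending of randomization".
- Section 7.1: "Rate of RVD at 48h randomized administration".

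The continuous indices (TAPSE, S', FAC, RVEDA/LVEDA and the rest) are secondary endpoints in section 2. Section 9(3) plans a CMH chi-square "test considering central effect was used for comparison between groups", with chi-square or Fisher tests for categorical variables and t or Wilcoxon tests for measurements. Inclusion criterion (4) in section 4.2 requires "Acute right ventricular dysfunction due to ARDS", so every patient has RVD at entry. No 48 h RVD rate is assumed for either arm.

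**The concern.** A mean difference and an SD are the inputs for comparing a continuous variable. The primary endpoint is yes/no per patient, and its variance is fixed by the event rate, so a sample size for it needs an assumed rate in each arm. Section 3.2 has none. A reader would still take 0.9 as the power for the primary comparison, since it is the only power in the document.

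Section 2 words the main objective as one to confirm. If the real power for RVD at 48 h is far below 0.9, a non-significant result could be misread as evidence of no effect from a well-powered trial.

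**Working it through.** **1. Reproduce the plan's figure.** Inputs from section 3.2: difference 20, SD 20, two-sided 0.05, power 0.9, 1:1.

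- Normal approximation: n = 2 × (1.960 + 1.282)² × (20/20)² = 21.0, so 22 per arm.
- t-test, noncentrality (20/20) × √(n/2): power is 0.8997 at n = 22 and 0.912 at n = 23, so 23 per arm.
- Dropout: 23 / 0.8 = 28.75, so 29 per arm and 58 in total.

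The stated 23, 29 and 58 come out exactly, as a t-test on a continuous variable.

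**2. Can the inputs describe a proportion?** A yes/no outcome has SD = √(p(1 − p)). Setting this to 0.20 gives p(1 − p) = 0.04, so p = (1 ± √0.84)/2 = 0.042 or 0.958. Two arms that share this SD have either the same rate or rates 91.6 points apart. They cannot be 20 points apart. For comparison, the SD is 40% at a rate of 80% and 49% at a rate of 60%.

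**3. Power for the RVD rate.** Assumption, not in the protocol: 20% means a 20-point absolute fall in RVD at 48 h. The control rate is not given, so a range is shown. Power is exact, by full enumeration of both binomial distributions at two-sided 0.05. Each cell gives uncorrected Pearson chi-square / Fisher; the last column is evaluable patients per arm.

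| Control vs levosimendan | Power, 23 per arm | Power, 29 per arm | n per arm for 90% power |
|---|---|---|---|
| 100% vs 80% | 70% / 50% | 86% / 54% | 32 / 45 |
| 90% vs 70% | 41% / 30% | 48% / 35% | 79 / 89 |
| 80% vs 60% | 32% / 22% | 38% / 28% | 108 / 117 |
| 60% vs 40% | 29% / 19% | 33% / 24% | 128 / 141 |

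The centre-stratified CMH test, simulated with three centres, gives the same range as chi-square: 29% to 70% with 23 per arm and 33% to 86% with 29. The pooled normal formula gives 46 per arm instead of 32 at 100% vs 80%. It is inaccurate at that extreme, so exact values are used.

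**4. Difference detectable at 90% power**, control rates 100% to 50%:

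| Evaluable per arm | Chi-square | Fisher |
|---|---|---|
| 23 | 27 to 46 points | 32 to 50 points |
| 29 | 22 to 42 points | 30 to 45 points |

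**The case against.** **The arithmetic in 3.2 is correct.** It is, for its own inputs. The fault is that those inputs belong to a different type of outcome from the primary endpoint.

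**The loss of power is hypothetical.** Section 3.2 never says that 20% is a fall in RVD, and a true fall of about 50 points would give 90% power even with 23 per arm. This stands as a limit on the figures: they are conditional. What does not depend on the assumption is that the protocol gives no valid power for its primary endpoint. If the 20% belongs to a continuous index, that endpoint has no sample-size basis at all. The protocol claims no larger effect.

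**High control rates are plausible.** All patients enter with RVD and any one criterion suffices, so the 48 h control rate may be near 100%, where power is best. That is fair, and it makes the lower rows of the table less certain to apply. Even so, chi-square power at 100% vs 80% is 70% to 86%, and at 95% vs 75% it falls to 51% to 62%. The 64% and 21% incidences in the background describe ARDS patients generally and do not supply a control rate here.

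**The test for the primary endpoint is not firmly fixed.** Section 9(3) lists several, and the choice matters. Power stays below 0.9 with chi-square, Fisher and CMH alike.

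**The wording about confirming is thin evidence.** It is one bracketed word in a translated sentence. The finding does not rest on it.

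**Conclusion.** The point holds. The 0.9 in section 3.2 is the power of a t-test for a standardised difference of 1.0 in an unnamed continuous variable. It does not carry over to the RVD rate at 48 h, for which no valid power is stated. That conclusion needs no outside assumption.

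The size of the shortfall does. Reading 20% as a 20-point fall, power is below 0.9 at every control rate checked from 100% to 50%, with either 23 or 29 per arm. At control rates of 90% or below it is under one half with either test, so such an effect would more likely be missed than found. This should be corrected before the power statement is relied on.

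**What to change.** In section 3.2:

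- Name the variable to which the 20% difference and 20% SD refer, and limit the power of 0.9 to it.
- For the RVD rate, state the assumed 48 h control rate, the test, the power that 23 and 29 per arm give for a 20-point difference, and the difference detectable at 90% power.

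In section 2, bring the wording of the main objective into line with that power. The abstract repeats 23, 29 and 58 but states no power, so nothing there becomes false.

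The cost is wording in two sections and no extra patients. The downside is a less favourable stated power for the primary endpoint. Keeping 0.9 for a 20-point fall in RVD would be a much larger change: 32 to 128 evaluable patients per arm by chi-square, or 45 to 141 by Fisher, across the four control rates in the table.
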